### 5.1.3. Enrollment Procedure

Along with the reports confirming the subject's primary diagnosis (Section 4.1), the investigator will check all the eligibility criteria (Section 4.3) of the subject based on all screening procedure results. This requires the availability and evaluation of the results of all screening procedures (Section 5.1.2). The investigator will then submit the Eligibility Verification Form (EVF) to the sponsor's medical monitor to approve the enrollment of the subject. Subjects will be provided with instructions on how to manage light exposure upon enrollment (Study Day 0).

### 5.2. Treatment Procedures

Treatment procedures will consist of three periods: Period I – PDT Course; Period II – Surgery; and Period III – Follow-up.

#### 5.2.1. Period I – PDT Course

##### *5.2.1.1. Study Day 1 (Photofrin® Injection)*

At the Study Day 1 visit, Photofrin® injection will be administered and the following assessments will be performed.

##### ***Prior to Photofrin® injection***

1. Reevaluate eligibility criteria.
2. Vital signs (pulse, blood pressure, temperature, and respiration rate).
3. Body weight.
4. Review instructions on how to manage light exposure.
5. Record concomitant medications and adverse events.

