#### 3.2. Scheduling of Visits

Pretreatment assessments will be performed during the 30 days prior to enrollment. After enrollment, study visits will be as follows:

- Study Day 0 will be the day the subject is enrolled.
- Study Day 1 will be the day of the PHO injection. Study Hour 0 will be the time of the end of PHO injection.
- Study Day 3 will be the day of PDT. Study Hour 40-50 will be calculated from Study Hour 0.
- Study Day 13 to Day 18 will be the time-period where the surgery will be performed post PDT.

- 
- Study Day 20 to Day 25 ( $\pm 2$  days) will be the 7-day post-surgery visit.
  - Study Day 43 to Day 48 ( $\pm 3$  days) will be the 30-day post-surgery visit.
  - Study Day 103 to Day 108 ( $\pm 7$  days) will be the 90-day post-surgery last study visit.

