### 4.3. Eligibility Criteria

#### 4.3.1. Inclusion Criteria

In order to be eligible to participate in the study, potential subjects must meet all of the following inclusion criteria.

1. Male or female subject is eighteen years of age and older (but less than 80 years of age).
2. Subject is diagnosed with primary or metastatic tumor < 5 cm located in peripheral lung that can be completely resectable (R0).
3. Subject is a candidate for surgical resection.
4. Subject is a candidate for bronchoscopy.
5. The tumor is accessible for unrestricted illumination of PDT.

6. Subject is deemed likely to survive for at least 3 months.
7. Non-menopausal or non-sterile female subject of childbearing potential has a negative serum  $\beta$ -HCG at the time of entry into the study.
8. Non-menopausal or non-surgically sterilized female subject of childbearing potential uses a medically acceptable form of birth control.
9. Subject is able and willing to provide written informed consent to participate in the study, which must comply with the International Council for Harmonisation (ICH) guidelines and local requirements.

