##### 4.6.1. Female Study Subjects

During the study, it is expected that females of childbearing potential will have to take appropriate measures to prevent pregnancy for 3 months after PDT, such as the use of medically acceptable contraceptive regimens namely:

- systemic contraceptives (e.g., transdermal patch, birth control pills, injectable or implantable or insertable hormonal birth control products);
- double-barrier method (e.g., diaphragm with intravaginal spermicide, cervical cap with intravaginal spermicide, condom with intravaginal spermicide, condom with diaphragm);  
or
- Intrauterine or intravaginal methods (e.g., vaginal contraceptive ring, intrauterine system with hormone release, copper intrauterine device).

Female subjects will be instructed to inform the investigator should a change in the contraceptive regimen occur during the study. Females of childbearing potential will be informed about this requirement in the ICF. Abstinence will not be considered as a medically acceptable contraceptive method.

Females who do not use an acceptable contraceptive regimen will be allowed to participate in this study only if they are not considered to be of childbearing potential: female who has had a hysterectomy, bilateral ovariectomy, or tubal ligation (performed during at least six months prior

to enrollment), is clinically diagnosed infertile, or is in a menopausal state (minimum of one year without menses). A female subject engaged with a vasectomized partner will not require an additional contraceptive method.

Should a case of pregnancy in female subject occur during the course of the study, the female subject will be monitored for the pregnancy outcome at birth, 6 months and 12 months following birth.

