### 5.1. Pretreatment Procedures

Pretreatment procedures (ICF and screening) will be performed during 30 days prior to enrollment. All procedures performed to confirm the primary diagnosis must be performed no more than 60 days prior to ICF signature.

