#### 5.3.2. Subjects who prematurely discontinued the study

##### *5.3.2.1. Early discontinuation due to consent withdrawal*

In case of withdrawal of consent, the date of withdrawing consent will be collected. If possible, the reason for withdrawing consent will be collected to exclude safety reason. No additional data will be collected from the time of consent withdrawal.

*5.3.2.2. Early discontinuation for reason other than withdrawing consent*

The investigator will make every effort to complete the following at the time of study discontinuation.

1. Reason for early discontinuation.
2. Comprehensive Physical Examination.
3. Vital signs (pulse, blood pressure, temperature, and respiration rate).
4. ECOG Performance Status.
5. Clinical labs (Appendix 13-4).
6. Serum  $\beta$ -HCG (only for female subjects of childbearing potential).
7. Concomitant medications and adverse events.

---

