5.4.11.2 Clinical Laboratory Parameters

Samples will be obtained for the clinical laboratory tests at the following time points: Screening, Hospital Discharge (Day 5) and Study Exit visits.

The following tests will be performed:

- Chemistry: Glucose (random), Blood urea nitrogen, Sodium, Potassium, Chloride, Creatinine, Alkaline Phosphatase, Aspartate Aminotransferase, Alanine Aminotransferase, Total bilirubin, Albumin, Total protein.
- Hematology: Hemoglobin, Hematocrit, White blood cell, Red blood cell, Platelet count, Prothrombin time

Additionally, samples for Serum β -HCG pregnancy test will be collected from women of childbearing potential only at Screening, Day 43-48 visit and Study Exist visit.

Laboratory results for chemistry and hematology as well as changes from baseline will be summarized descriptively by visit. Only subjects with both non-missing baseline and time point values will be summarized at each time point.

Shifts among normal, low and high results (as determined by laboratory normal ranges) from baseline to last available post-baseline assessment will be summarized.

All individual subject clinical laboratory results will be presented in listings by subject and visit. Results of the pregnancy test will be listed.

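### The only required pre-dose serum beta-HCG is the screening sample, with no limit on its age at injection, so the single Photofrin dose may rest on a result up to 31 days old

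*Protocol*

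**What the plan says.** Serum beta-HCG is a screening procedure for women of childbearing potential (Protocol 5.1.2, item 11). It appears again at the 30-day and 90-day post-surgery visits (5.2.3.2 and 5.2.3.3). Appendix 13-1 and SAP Table 1 mark the same three columns. SAP 5.4.11.2 agrees: samples are "collected from women of childbearing potential only at Screening, Day 43-48 visit and Study Exist visit". One further test is listed at early discontinuation for reasons other than withdrawn consent (5.3.2.2), where "The investigator will make every effort to complete the following at the time of study discontinuation".

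The screening window is tied to enrollment, not to dosing: "Pretreatment procedures (ICF and screening) will be performed during 30 days prior to enrollment" (5.1). Section 3.2 fixes the calendar: "Study Day 0 will be the day the subject is enrolled", and the injection is on Day 1.

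Inclusion criterion 7 asks for a negative serum beta-"HCG at the time of entry into the study" (4.3.1), without a sample age in days. Enrollment is decided on screening data: "This requires the availability and evaluation of the results of all screening procedures" (5.1.3). On Day 1, the pre-injection list in 5.2.1.1 has five items: "Reevaluate eligibility criteria", vital signs, body weight, light-exposure instructions, and recording of medications and adverse events.

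Contraception is covered by inclusion criterion 8 and by section 4.6.1: "During the study, it is expected that females of childbearing potential will have to take appropriate measures to prevent pregnancy for 3 months after PDT". Abstinence does not count as a method there, and subjects are told to report a change of regimen.

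**The concern.** Photofrin is given once (Synopsis, Duration of Treatment), so a pregnancy already under way can be kept from exposure only if it is found before the Day 1 injection. A negative result from the start of the screening window does not exclude a pregnancy that began afterwards, and the plan calls for no later sample before dosing. Where the protocol wants a fresh Day 1 measurement it lists one, as with vital signs and body weight; beta-HCG is not listed.

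If a pregnancy were missed, the fluoroscopy-guided procedure on Day 3 and the chest CT and surgery on Days 13 to 18 would also come before the next scheduled test. The protocol itself treats pregnancy as important: it is an example of a significant violation in section 4.7 and is reportable within 24 hours under 8.4.3.3. The documents give no figure for fetal risk, so the size of the harm is not estimated here.

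**Working it through.** **Inputs.** Screening runs from Day -30 to Day -1 (Appendix 13-1). Enrollment is Day 0, injection Day 1 and PDT Day 3 (3.2). Surgery is 10 to 15 days after PDT (3.1). The next scheduled beta-HCG is at the Day 43-48 visit, with a window of 3 days either way (5.2.3.2).

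**Check of the day count.** The plan states no sample age, so I first confirmed that plain day subtraction reproduces its calendar.
- Surgery: 3 + 10 = 13 and 3 + 15 = 18, giving Days 13-18.
- Adding 7, 30 and 90 days gives Days 20-25, 43-48 and 103-108. All match section 3.2.

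**Sample age at injection** = 1 - (screening day).
- Oldest permitted: 1 - (-30) = 31 days.
- Most recent: 1 - (-1) = 2 days.

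**Injection to next scheduled test.**
- Nominal: 43 - 1 = 42 to 48 - 1 = 47 days.
- With the window: 40 - 1 = 39 to 51 - 1 = 50 days.
- Longest interval between the screening test and the next scheduled test: 51 - (-30) = 81 days.

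**Effect of the numbering convention.** The study-day formula in SAP 5.1 has no Day 0, so protocol Day -30 becomes SAP Day -31. The elapsed time is still 31 days. Only if the Day -30 label were itself read in SAP numbering would the maximum be 30 days.

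**Does the text force a newer sample?** Inclusion 7 refers to entry into the study, and 5.1.3 bases enrollment on screening results, so a screening negative satisfies the criterion. The Day 1 re-check asks for the criteria to be looked at again but names no test. Neither Appendix 13-1 nor SAP Table 1 marks beta-HCG on Day 0 or Day 1. A site may choose to repeat the test, but nothing obliges it to.

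**Which screening draws would meet a limit.** Draw and injection can fall at any hour of their days.
- 72 hours: Day -1 to Day 1 is two calendar days, so at most 3 x 24 = 72 hours; a Day -1 draw always qualifies. Day -2 to Day 1 is three calendar days: a draw at 08:00 and an injection at 10:00 are 74 hours apart and fail. A Day -2 draw works only if taken no earlier in the day than the injection.
- 7 days (168 hours): Day -5 to Day 1 is six calendar days, so at most 7 x 24 = 168 hours. Any draw from Day -5 to Day -1 qualifies.

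The maximum sample age would fall from 31 days to 3 days with the 72-hour limit, or to 7 days with the one-week limit.

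**The case against.** The best defence is that the plan already has several safeguards. There is a pre-dose test. Eligibility is re-evaluated on Day 1, which takes in inclusion 7 and inclusion 8. Acceptable contraception is required, abstinence is not accepted as a method, and changes of regimen must be reported. A careful site could read the Day 1 re-check as a reason to repeat the test. These points stand as risk reduction. They do not make a current sample mandatory, and contraception does not detect a pregnancy; the protocol evidently does not treat it as enough alone, since it also tests at screening.

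The second objection is that any particular limit is a choice. That stands: the documents do not determine 72 hours or 7 days.

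The third is proportion. The subgroup is small and may be empty, no analysis changes, and an amendment is a real burden. Planned enrollment ran to Q1 2018 and the SAP is dated 10 April 2018, so on the planned timeline dosing may already have finished; actual dates are not given. This supports a low priority but does not remove the gap.

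A reader might infer more: that no pregnancy test precedes dosing, or that inclusion 7 contradicts the schedule. The documents support neither. The screening test is required, and its result reviewed at enrollment meets the criterion as worded. The defect is the permitted age of the sample.

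**Conclusion.** The point holds as a timing gap in subject protection. A compliant site may inject on a negative beta-HCG up to 31 days old, and the next scheduled test comes 39 to 50 days after the only dose. An earlier test is listed only for early discontinuation, and no test after dosing can undo the exposure.

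The 31 days assumes injection on the calendar day after enrollment, as the numbering implies. No separate limit on that interval is stated, and any delay would add to the sample age day for day.

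The weight is low. Only women of childbearing potential are concerned; their number among about 10 subjects is not given and may be zero. No endpoint, confidence limit or planned analysis is affected. It is a worthwhile improvement, not an error in the statistical plan.

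**What to change.** Leave inclusion 7 as it is. Add an item to the pre-injection list in Protocol 5.2.1.1: for females of childbearing potential, confirm a negative serum beta-HCG on a sample drawn within a stated limit before injection, with the result available before dosing; do not inject if positive; a screening sample within the limit counts. The limit could be 72 hours, which is an assumed figure; up to 7 days is reasonable. Add a matching Day 1 footnote in Appendix 13-1.

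The choice of limit has a practical side. With 72 hours, only a Day -1 draw, or a Day -2 draw timed late enough, can serve both purposes, and the result must be back for the Eligibility Verification Form and the medical monitor's approval before Day 0. With 7 days, the screening draw is easier to place, and a positive is found before enrollment.

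In the SAP, only the schedule table needs to match. Pregnancy results are simply listed, and SAP 5.1 already puts every timepoint with data into the listings.

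The cost is at most one blood test per affected subject, or none if the screening draw is well timed, and a possible short wait for the result. It also needs a protocol amendment: section 11.9 counts an added safety test among changes requiring IRB approval at all centers and regulatory approval. A subject found positive only on Day 1 would be in the ITT but not the Safety Population. If she were not replaced, Safety N would be 9 and the zero-event upper limit 1 - 0.05^(1/9) = 0.28, against 1 - 0.05^(1/10) = 0.26. Drawing before enrollment, inside the limit, avoids this.

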##### ***Photofrin® injection***

1. Subjects will receive Photofrin® at a dose of 2 mg/kg as a single, slow IV injection lasting 3–5 minutes corresponding to approximately 5 mL every 15 seconds. It may be administered through the “Y” tube of an IV administration set. It cannot be mixed with other drugs. Precautions should be taken to prevent extravasation at the injection site. If

extravasation occurs, care must be taken to protect the area from light. There is no known benefit from injecting the extravasation site with another substance. Further information on reconstitution and administration of PHO can be found in Section 6.1.3 and in the Pharmacy Manual.

2. Vital signs (pulse, blood pressure, temperature, and respiration rate) at 15 minutes, 30 minutes, 1, 2, 4, and 8 hours after the injection.
3. After the injection, subjects will be asked general questions about how they feel. Any occurrence of adverse events and need of concomitant medication will be recorded.

#### *5.2.1.2. PDT Bronchoscopy (Study Day 3, 40-50 Hours post Photofrin® injection)*

Subjects will return to the institution on Study Day 3 (40-50 hours post Photofrin® injection) for the PDT bronchoscopy procedure. The following assessments will be performed.

1. Vital signs (pulse, blood pressure, temperature, and respiration rate).
2. ECOG Performance Status.
3. Under general anesthesia or deep sedation
  - a. Subjects will undergo a flexible bronchoscopy with navigation guidance to confirm the location and the size of the lesion with the use of radial probe endobronchial ultrasonography (REBUS). This will be captured by video.
  - b. The investigator will select the optical fiber diffuser length to match the tumor length.
  - c. Once the desired placement of the probe is confirmed by REBUS, the investigator will remove the REBUS probe and will insert the selected optical fiber in the lesion under fluoroscopy guidance. This will be captured by video. Exceptionally, the placement of the diffuser adjacent to the tumor for intraluminal activation will be acceptable only if the placement of the optical diffuser in the lesion has been unsuccessful. For larger lesions than 1.5 cm the placement of multiple fibers from different directions will be allowed if feasible.
  - d. After the placement of the optical fiber in the lesion, the 630 nm PDT laser will be turned on and will deliver a light dose of 200 J/cm of diffuser length for an exposure time of 8 minutes and 20 seconds using a pre-set total power output. Subjects presenting multiple metastases, only one lesion would be treated.
4. Re-educate the subject on how to manage light exposure.
5. Record concomitant medications and adverse events.
6. Admit subject for a 48-hour hospitalization period.

#### *5.2.1.3. Study Day 5 (Hospital Discharge Evaluation)*

Approximately 48 hours after PDT bronchoscopy, the following safety evaluations will be performed to determine if subjects are medically stable to be discharged from the hospital.

1. Vital signs (pulse, blood pressure, temperature, and respiration rate).

2. Clinical labs (Appendix 13-4).
3. Chest X-ray.
4. Record concomitant medications and adverse events.

*5.2.1.3.1. Subject medically stable*

Discharge subject and provide instructions on how to manage light exposure.

*5.2.1.3.2. Subject non-medically stable (Day 6 to Day 10 -Extended hospitalization as required)*

The subject's 48-hour hospitalization can be extended to 72 hours (or longer) at the discretion of the investigator if the subject is deemed medically unstable. During this extended hospitalization, the following assessments should be performed daily until the subject is considered stable and able to be discharged.

1. Vital signs (pulse, blood pressure, temperature, and respiration rate).
2. Record concomitant medications and adverse events.

The day of the discharge, the following assessments should be performed.

1. Clinical labs (Appendix 13-4).
2. Chest X-ray.

The prolongation of hospitalization after 72 hours due to subject being medically unstable is to be reported to the sponsor as a serious adverse event. If a subject is still hospitalized at Day 10, the sponsor should be notified promptly.

*5.2.2. Period II - Surgery (Study Day 13 to Day 18)*

All subjects will undergo surgery as per standard of care 10 to 15 days after PDT. The following assessments will be performed.

***Prior to surgery***

1. Vital signs (pulse, blood pressure, temperature, and respiration rate).
2. ECOG Performance Status.
3. Chest CT scan.
4. Record concomitant medications and adverse events.

***Surgery and post-surgery care***

1. Surgery and post-surgery care as per standard of care.
2. Reduced light settings and subject draping will be used to avoid potential problems from bright surgical lights:
  - from the moment the subject enters the hospital and will continue while the subject is in the surgical suite and on the surgical care units;

- surgery will be performed with room lights which are modified by amber filters that block wavelength below 550 nm;
- incisions will be shielded from inadvertent light exposure (e.g., sterile blue towels);
- remainder of the subject's skin will be draped in the usual surgical manner.

In addition, measuring oxygen saturation with pulse oximetry (pulse ox) will expose the skin to red light, which may cause skin burns if left in one place too long. Continuous monitoring can be carried out by setting up multiple monitors and rotating on and off status of the fixed sensors, or by moving a single sensor to different pulsating arteriolar bed, such as the finger, great toe, nose, or earlobe.

3. Record concomitant medications and adverse events.
4. Macroscopic and microscopic examinations of lung tumor tissue and lung healthy tissue. Lung tissue following surgical resection will be sent to the local pathology lab for macroscopic examination. Slides for microscopic examination will be prepared by the local pathology lab and sent to an independent expert pathologist (ARUP Laboratories, Salt Lake City, UT, USA) for central reading. The central assessor will interpret all histology samples obtained through surgery across all sites. Procedures for slide preparation and shipment will be performed as per laboratory instructions provided to participating sites.
5. Re-educate the subject on how to manage light exposure.

### 5.2.3. Period III - Follow-Up

#### 5.2.3.1. 7-Day Post-Surgery Visit (Study Day 20 to Day 25 [ $\pm 2$ days])

Subjects will undergo the following evaluations.

1. Vital signs (pulse, blood pressure, temperature, and respiration rate).
2. ECOG Performance Status.
3. Chest X-ray.
4. Re-educate the subject on how to manage light exposure and train the subject on how to perform the Light Challenge procedures at home the day before the next visit (Section 7.1).
5. Record concomitant medications and adverse events.

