#### 5.2.3.2. 30-Day Post-Surgery Visit (Study Day 43 to Day 48 [ $\pm 3$ days])

Subjects will undergo the following evaluations.

1. Vital signs (pulse, blood pressure, temperature, and respiration rate).
2. ECOG Performance Status.
3. Chest CT scan.
4. Serum  $\beta$ -HCG (only for female subjects of childbearing potential).
5. Record the result of the Light Challenge.

6. Re-educate the subject on how to manage light exposure based on the result of the Light Challenge.
  - If the subject passes the Light Challenge, the subject will be instructed to gradually resume normal outdoor activities, initially continuing to exercise caution and gradually allowing increased exposure.
  - If the subject does not pass the Light Challenge, the subject will be instructed to continue adhering to light restrictions and repeat the Light Challenge in 14 days. The Light Challenge should be repeated every 14 days until passed.
7. Record concomitant medications and adverse events.

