## 7. WARNINGS AND PRECAUTIONS

### 7.1. Phototoxicity Reactions

All subjects who receive Photofrin® will be photosensitive and must observe precautions to avoid exposure of eyes and skin to direct sunlight or bright indoor light (from examination lamps, including dental lamps, operating room lamps, unshaded light bulbs at close proximity, etc.) for at least 30 days or longer as per local labelling.

The level of phototoxicity will vary for different areas of the body, depending on the extent of previous exposure to light. Before exposing any area of skin to direct sunlight or bright indoor light, the subject should perform the Light Challenge to test the skin for residual phototoxicity. A small area of skin (e.g., hand) should be exposed to sunlight for 10 minutes. If no phototoxicity reaction (erythema, edema, blistering) occurs within 24 hours, the subject can gradually resume normal outdoor activities, initially continuing to exercise caution and gradually allowing increased exposure. If a phototoxicity reaction occurs with the limited skin test, the subject should continue the existing precautions for another 2 weeks before re-testing. As the tissue surrounding the eyes may be more sensitive, it is therefore not recommended that the face be used for testing. If subjects travel to a different geographical area with greater sunshine, they should retest their level of phototoxicity. Ultraviolet (UV) sunscreens are of no value in protecting against phototoxicity reactions because photoactivation is caused by visible light.

Some subjects may remain photosensitive for up to 90 days or more. The photosensitivity is due to residual drug, which will be present in all parts of the skin. Exposure of the largest possible area of skin to ambient indoor light is, however, beneficial because the remaining drug will be inactivated gradually and safely through a photobleaching reaction. Therefore, subjects should not stay in a darkened room during this period and should be encouraged to expose their skin to ambient indoor light.

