### 7.3. Training and Instructions

Members at each site will be trained by the sponsor-designated representatives to ensure knowledge of subject safety issues prior to recruitment of the first subject. All subjects will be seen in clinic prior to scheduling the procedure and will be educated on the risks and benefits of the intervention and educated on the preventive measures to avoid cutaneous phototoxicity. Subjects will also be given a "Patient Kit", which includes gloves, sunglasses, hat with neck protection, and instructions on how to manage light exposure. Subjects will be encouraged to

[figure not shown]
expose their skin to ambient indoor light. Subjects will not be considered for the study if the clinician deems that the subject is not mentally capable of following instructions to prevent phototoxicity.

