#### 8.4.1. Assessment and Recording

An AE, whether or not considered to be causally related to the treatment, must be promptly documented and recorded. At each study visit, after the subject has had an opportunity to spontaneously mention any problems, the investigator should inquire about AEs by asking the appropriate open questions. In addition to straightforward subject observation (e.g., headache, nausea, etc.), AEs will also be documented from any data collected in the CRF (e.g., laboratory values, physical examination findings, ECG changes, etc.) or other documents that are relevant to the safety of the subject.

At each follow-up visit or assessment by phone or otherwise, all AEs, whether observed by the investigator or other professional collaborators, or reported by the subject spontaneously or in response to an open question, will be recorded on the Adverse Event Form included in the CRF with the following information.

- Name of the AE: Name should be a medical term. When possible, the investigator should differentiate an illness entity from isolated symptoms or signs. For instance, the term “flu” should be recorded instead of listing all the flu-related symptoms. Where a differentiation is not possible, symptoms and signs should be separately recorded and evaluated as adverse events.
- Date of onset of the AE.
- Intensity: Event intensity will be assessed according to the CTCAE. If not described in the CTCAE, the intensity should be assessed according to the following categories: *Mild* (noticeable to the subject, does not interfere with the subject’s daily activities, usually does not require additional therapy, dose reduction, or discontinuation of the study); *Moderate* (interferes with the subject’s daily activities, possibly requires additional therapy, but does not require discontinuation of the study); *Severe* (severely limits the subject’s daily activities and may require discontinuation of the study); *Life-threatening*; *Death*.
- Date of resolution (or statement that the event is continuing).
- Action taken (e.g., concomitant medication or adjunctive therapy given will be recorded on the Concomitant Medications Form or the Adjunctive Therapy Form of the CRF, respectively).
- Outcome defined as resolved, resolving, ongoing, worsening, death, or unknown.
- Whether the event meets the definition of a SAE (see Section 8.1).

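### The Light Challenge is scheduled one calendar day before the visit at which it is recorded, which does not guarantee the 24 hours that a pass requires, and no step returns a late reading to the site

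*Protocol*

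**What the plan says.** Four places in the Protocol and one in the SAP bear on this.

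- **When the test is done.** Protocol 5.2.3.1 (item 4) has the site "train the subject on how to perform the Light Challenge procedures at home the day before the next visit" and refers to Section 7.1. It sets no time of day.
- **What the test is.** Protocol 7.1: "A small area of skin (e.g., hand) should be exposed to sunlight for 10 minutes".
- **What counts as a pass.** Protocol 7.1: "If no phototoxicity reaction (erythema, edema, blistering) occurs within 24 hours, the subject can gradually resume normal outdoor activities". If a reaction does occur, the subject keeps to the precautions for two more weeks and retests.
- **What happens at the visit.** Protocol 5.2.3.2 (Day 43 to 48, ±3 days) lists "Record the result of the Light Challenge" and then the advice that depends on it: "If the subject passes the Light Challenge, the subject will be instructed to gradually resume normal outdoor activities". After a fail, restrictions stay and the test is repeated every 14 days. There is no third branch for a test still running.
- **Analysis.** SAP 5.4.13 says only that the challenge is done at home before the Day 43-48 visit and that results are listed.

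The schedule (Protocol Appendix 13-1) marks the Light Challenge at Day 43-48 only. The next scheduled visit is Study Exit, Day 103 to 108 (±7 days). Its procedures (Protocol 5.2.3.3) include light-exposure re-education if needed and adverse event recording, but not a Light Challenge result.

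**The concern.** A lead of one calendar day is not a lead of 24 hours. A subject who tests in the afternoon and attends the next morning has followed Section 5.2.3.1 exactly, yet the Section 7.1 observation period has not ended when the site comes to record the result. If a reaction is already visible, the test has failed and nothing is lost. If the skin is still clear, the result is not yet known, and Section 5.2.3.2 offers only pass or fail.

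The reading decides whether the subject is advised to start easing light restrictions. Section 7.1 says photosensitivity can last 90 days or more in some subjects, so a positive test at this time is possible and the test is not a formality. A pass entered too early would also appear in the SAP listing with nothing in the protocol or SAP to mark it as early.

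**Working it through.** The plan gives no figure to reproduce. The check is clock and calendar arithmetic.

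**Hours elapsed at the reading.** Let *e* be the clock hour of the exposure on the day before, and *v* the clock hour of the visit.

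Elapsed = 24 + *v* − *e*

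This is below 24 exactly when *e* > *v*. Counting from the end of the 10-minute exposure takes off about 0.17 h and changes nothing of substance.

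The documents give no clock times, so the following are assumptions for illustration. With both *e* and *v* between 8 and 17:

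- shortest: 24 + 8 − 17 = 15 h
- longest: 24 + 17 − 8 = 33 h

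| Visit | Exposure 08:00 | Exposure 12:00 | Exposure 16:00 |
|---|---|---|---|
| 08:00 | 24 h | 20 h | 16 h |
| 09:00 | 25 h | 21 h | 17 h |
| 10:00 | 26 h | 22 h | 18 h |
| 15:00 | 31 h | 27 h | 23 h |

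For a 09:00 visit, an 08:00 exposure is fully read and a 16:00 exposure is 24 − 17 = 7 h short. The share of subjects read early depends on the distribution of both times, which cannot be had from the documents.

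**The same hours with a two-day lead.** Elapsed = 48 + *v* − *e*. The range becomes 48 + 8 − 17 = 39 h to 48 + 17 − 8 = 57 h. Because *v* − *e* is always greater than −24, elapsed time exceeds 24 h for any clock times at all.

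**Where the test falls after injection.** Injection is Day 1, so days after injection = study day − 1.

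- Visit, with window: Day 43 − 3 = 40 to Day 48 + 3 = 51.
- Challenge one day before: Day 39 to 50, which is 38 to 49 days after injection.
- Challenge two days before: Day 38 to 49, which is 37 to 48 days after injection.

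Section 7.1 requires precautions "for at least 30 days or longer as per local labelling". The two-day lead stays at least 37 − 30 = 7 days past that 30-day minimum.

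**Time to the next scheduled contact.** For one subject the 30-day visit is surgery + 27 to 33 days and Study Exit is surgery + 83 to 97 days. The gap is nominally 90 − 30 = 60 days, and from 83 − 33 = 50 to 97 − 27 = 70 days with the windows.

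**The case against.** The strongest answer is that the subject, not the clinic, reads this test. Section 5.2.3.1 trains the subject on Section 7.1, which has the subject perform the test, watch for a reaction over 24 hours and act on what is seen. A subject seen at 17 hours can complete the other 7 at home. This stands. It does not supply a route by which the final reading reaches the site, replaces an entry already made, or changes advice already given.

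A reader might infer that the plan directs sites to ease restrictions too soon. It does not. The advice in Section 5.2.3.2 is conditional on a pass, and Section 7.1 defines a pass by 24 hours, so a careful site would hold the result or tell the subject to wait. Releasing the subject early would depart from those sections.

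A reader might also infer that the day-before timing leaves the subject unsupervised for about 60 days. That gap is not specific to an early reading: subjects who fail also repeat the test at home with no visit scheduled for the repeats.

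A third tempting inference is that the photosensitivity analysis is compromised because skin photosensitivity is the named adverse event of special interest. The documents do not support it. The challenge is not an endpoint. Photosensitivity is summarized from adverse events (Protocol 10.5.3, SAP 5.4.11.1), which are collected throughout the study, and a late reaction can still be recorded at Study Exit.

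Finally, the material given to subjects may fix a time of day. Section 7.3 mentions a kit with "hat with neck protection, and instructions on how to manage light exposure", and Section 10.2 an eCRF completion guideline. Neither is among the documents; the protocol and SAP themselves set no time.

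**Conclusion.** The mismatch is in the text and needs no assumption: one calendar day can be less than 24 hours, and the result is recorded and acted on at the visit. What is missing is narrow, namely a step that brings a reading completed after the visit back to the site and revisits a pass or advice already given.

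The practical effect is minor. It concerns the safety advice at one visit and a result that is only listed; no endpoint, confidence limit or adverse event table depends on it. A pass permits only cautious, stepwise exposure, 38 days or more after injection, and a subject who then reacts is told to return to precautions. The 15-to-33-hour range rests on assumed clock times, and the frequency of early readings is unknown. The point is worth acting on because the remedy is nearly free and lets a safety reading meet the protocol's own definition.

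**What to change.** Change item 4 of Protocol 5.2.3.1 so that the Light Challenge is done two days before the 30-day post-surgery visit, or state directly that it must be done at least 24 hours before the reading. The SAP wording already fits a two-day lead and needs no change.

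Alternatively, keep the day-before timing and add a line to Section 5.2.3.2: if 24 hours have not passed at the visit and no reaction has appeared, restrictions continue until they have, and the site confirms the result by phone before recording it. Telephone contact is already foreseen for adverse events (Section 8.4.1: "At each follow-up visit or assessment by phone or otherwise, all AEs").

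The cost is one changed subject instruction or an occasional call. Recording the date and time of exposure and of reading would let a reader of the listing confirm the interval, but it is optional for a result that is only listed.
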